### **Introduction:**

In December 2019, health authorities in Wuhan, Hubei province, China issued an epidemiological alert for an outbreak of pneumonia of unknown causes, the infected patients had in common having visited a local seafood and wild animal market.

At the beginning of the outbreak, samples from seven patients with severe pneumonia in the intensive care unit (ICU) of Wuhan Jin-Yin-Tan Hospital were obtained for analysis by the Wuhan Institute of Virology (WIV) to isolate the pathogen causing the disease. After studying the samples received, the WIV identified a new coronavirus as responsible for the outbreak, which shares 79.6% similarity to the genomic sequences of SARS-CoV and 96% similarity to those of a bat coronavirus. Based on the phylogenetic and taxonomic characteristics of the virus, the International Committee on Taxonomy of Viruses officially named the newly detected virus; severe acute respiratory syndrome coronavirus type 2 (SARS-CoV-2) and the disease caused by this virus has been termed; Coronavirus disease 2019 (COVID-19), an extremely contagious respiratory infection.

In an attempt to contain the epidemic, the Chinese government took a series of measures to prevent the displacement of millions of people inside and outside the country; however, many of them have already left the country to go on vacation to other places to celebrate the traditional Chinese New Year. On January 30, 2020, the World Health Organization (WHO) announced that the SARS-CoV-2 pneumonia outbreak was a global health emergency and on March 11 declared the disease COVID-19 a pandemic. As of August 26, 2021, 213,752,662 confirmed cases and 4,459,381 deaths have been reported worldwide; in Mexico, 3,291,761 total cases and 256,287 total deaths due to COVID-19 have been reported. For this reason, the WHO has created a database containing the results of research on COVID-19

conducted by scientists and health professionals from around the world, which has allowed accelerating the processes of diagnosis, treatment and vaccine development.

According to the information provided by WHO, it is vital to continue research to answer a number of questions about the vaccines currently in use, which have been licensed for emergency use to combat the COVID-19 pandemic. One of the most worrisome questions concerns the duration of the immunity conferred by these vaccines and, moreover, whether they will protect the population from the new SARS-CoV-2 strains that continue to appear.

### **General description of coronaviruses**

Coronaviruses (CoVs) belong to the Coronaviridae family and consist of an envelope and a single strand of positive-sense, non-segmented ribonucleic acid (RNA). The genomic organization of all CoVs is similar; the non-structural proteins are encoded within the two thirds of the 5' end and the structural proteins called; spike (S), envelope (E), membrane (M) and nucleocapsid (N) are encoded in the 3' third. The name coronavirus is due to the characteristic crown-like appearance of the virions, this morphology is given by the spike-shaped proteins embedded in the envelope. Based on their phylogenetic properties, CoVs are divided into four genera; group 1 (alpha-CoV), group 2 (beta-CoV), group 3 (gamma-CoV), group 4 (delta-CoV).

This family of viruses has been known since the 1930s, they were identified as pathogens responsible for infectious diseases in farm animals, and they are also responsible for diseases in a wide variety of animals including humans.

Before SARS-CoV-2 appeared, six species of coronaviruses were already known to cause disease in humans, four of which cause mild symptoms of the common cold in non-immunocompromised individuals. The other two strains are of zoonotic origin;

SARS-CoV, responsible for outbreaks of severe respiratory syndrome in 2002 and 2003, and MERS-CoV, which caused severe respiratory illness in the Middle East in 2012.

### **Genomic structure of SARS-CoV-2**

The structural proteins of SARS-CoV-2 play a key role in the interaction of the virus with host cells. The S protein consists of two subunits, S1 and S2. The S1 subunit contains the receptor binding domain (RBD) that binds to the host cell receptor, while the S2 subunit facilitates fusion of the viral envelope with the cell membrane. Angiotensin converting enzyme type 2 (ACE-2) has been identified as the main receptor for SARS-CoV-2, this receptor is predominantly expressed on type II pneumocytes, airway epithelium, digestive tract, endothelium, kidney, fibroblasts, and various immune cells. The M protein confers structure to the virus, once bound to the nucleocapsid it regulates virus assembly, and also contains T-cell epitopes that trigger the production of neutralizing antibodies in infected individuals. The E protein is essential for the assembly, release and pathogenesis of the virus. The N protein is key in the formation of complexes with the viral genome, enhances the functions of the M protein and increases viral replication.

### **COVID-19**

COVID-19 is defined as the disease caused by the new SARS-CoV-2 coronavirus. The main mechanism of transmission is by the airborne route through contact with flung droplets and aerosols that are released by an infected person when talking, coughing or sneezing, especially in crowded, closed and poorly ventilated places. Other means of spreading the virus are: contact with objects or surfaces containing the virus, constant touching of the face (eyes, nose or mouth) as well as shaking hands with an infected person.

The incubation period varies between 5 and 7 days. The clinical presentation is not specific; it can range from asymptomatic to extremely severe. The most common symptoms are fever, nonproductive cough, muscle pain, fatigue and dyspnea; some patients may also present with headache, nausea and diarrhea, especially early in the course of infection, prior to the onset of fever. Recent studies indicate that the severity of the disease correlates with age (> 60 years) and with the presence of underlying diseases (hypertension, diabetes, heart disease); these groups of patients are at higher risk of developing acute respiratory distress, pneumonia and even death. Several tests are currently available for the diagnosis of COVID-19, but the reverse transcriptase polymerase chain reaction (rt-PCR) test is the gold standard diagnostic technique.

## **Vaccines and COVID-19**

To date, there is no specific treatment for COVID-19. For this reason, efforts have focused on preventing the spread of the disease through mitigation measures and on seeking herd immunity, also known as flock immunity, through vaccination. Research conducted after the SARS-CoV epidemic in 2003 has laid the groundwork for the development of vaccines against COVID-19, due to the genetic similarity shared by both CoVs.

Historically, the implementation of vaccination programs, especially during childhood, has been the key to controlling and/or eradicating countless infectious and contagious diseases. Vaccines prepare the immune system to create immunoglobulins that can later recognize the pathogen in question and attack it, thus breaking the chain of disease transmission.

As of June 3, 2021, WHO has assessed that the following COVID-19 vaccines meet the criteria of safety and efficacy for population use.

## **Based on viral vectors**

### **- Oxford/AstraZeneca (ChAdOx1 nCoV-19)**

It is a vaccine that uses the chimpanzee adenovirus ChAdOx1 as a vector, expressing the S protein of SARS-CoV-2. According to data provided by the WHO and other studies, the vaccine has an efficacy of 63.09% against symptomatic SARS-CoV-2 infection. It is recommended to apply two doses of 0.5 ml each by intramuscular route with an interval of 8 to 12 weeks. It was authorized by the Federal Commission for Protection against Sanitary Risks (COFEPRIS) on January 4, 2021 for use in Mexico.

### **- Janssen (Ad26.COV2-S)**

This is a single-dose vaccine using a non-replicating adenoviral vector of serotype 26 containing the S protein of SARS-CoV-2. Phase 3 results published by Johnson&Johnson Pharmaceuticals indicate that the efficacy of the Janssen vaccine against moderate to severe COVID-19 infection was 72% in the United States of America, 66% in Latin America and 57% in South Africa 28 days after inoculation. The WHO Strategic Advisory Group of Experts (SAGE) recommends a dose of 0.5 ml administered intramuscularly. COFEPRIS authorized its use in Mexico on May 27, 2021.

## **Based on nucleic acids**

### **- Pfizer BioNTech (BNT162b2)**

This vaccine contains the mRNA coding for the S protein of SARS-CoV-2. According to the results of a multinational trial to assess the efficacy and safety of BNT162b2, it was concluded that after administration of two doses of 0.3 ml respectively 21 days apart, the efficacy was 95% against symptomatic infection caused by SARS-CoV-2 in persons older than 16 years of age. WHO recommends administering two doses 21 to 28 days apart, COFEPRIS authorized its use in Mexico on December 11, 2020.

### **- Modern (mRNA-1273)**

Like the previous one, it contains the mRNA encoding the S protein of SARS-CoV-2 encapsulated in lipid nanoparticles. Phase 3 trials for the mRNA-1273 vaccine showed 94.1% efficacy in preventing severe COVID-19 infection that can be observed after day 14 of the first application. WHO recommends the use of two doses of 0.5 ml each with an interval of 28 days. In Mexico, its use was authorized by COFEPRIS on August 17, 2021.

## **Based on inactivated viruses**

### **- Sinovac (CoronaVac)**

It is a vaccine formulated based on incubation of SARS-CoV-2 (CN02 strain) in Vero cells. A Phase 3 trial conducted in Turkey tested the efficacy and safety of this vaccine in volunteers between 18 and 59 years of age. The double-blind, randomized, placebo-controlled study concluded that the vaccine confers good humoral response against SARS-CoV-2, as well as high efficacy against symptomatic COVID-19 confirmed by PCR. It reports 51% efficacy against SARS-CoV-2 infection, 100% efficacy against severe infection and 100% efficacy against hospitalization from day 14 after receiving the second dose. The SAGE recommends applying two doses of 0.5 ml intramuscularly with a separation of 2 to 4 weeks between the first and second dose. In Mexico, COFEPRIS authorized its use as of February 9, 2021.

### **- Sinopharm (COVID-19 inactivated vaccine, Vero cells)**

It uses the same inactivation process as Sinovac but using the HB02 strain of SARS-CoV-2. A multi-country Phase 3 trial demonstrated 79% efficacy against symptomatic SARS-CoV-2 infection 14 days after the second dose. WHO recommends the application of 2 doses of 0.5 ml respectively, with a separation of 3 to 4 weeks between the first and second dose. It was recently approved by COFEPRIS on August 25, 2021 for use in Mexico.

## **Justification**

Currently, the pandemic originated by COVID-19 continues to be a serious public health problem in our country (Mexico) that implies a great investment by the federal government to combat the ravages caused by it, so it is of vital importance to determine the explicit mechanisms by which the different vaccines administered in our population have their protective effects on the virus infection. Therefore, this study focuses on identifying the molecular mechanisms by which inhibitions of virus recognition by the human host cell are carried out.

## **Problem Statement**

The precise mechanism by which a vaccinated patient has a high probability of being infected with a different strain of SARS-CoV-2 is currently unknown. Assuming this, recontagion and further increases in the rates of active cases of COVID-19 in the vaccinated population are not prevented. Therefore, by determining the molecular mechanisms of infection, therapeutic targets can be identified, and specific treatments can be offered to prevent infection in both first-contact subjects and those with a history of COVID-19 infection.

## **Hypothesis**

Gene expression for IgG anti-spike in subjects with a complete vaccination schedule against COVID-19 does not develop the necessary immunogenicity in the Mexican population to prevent re-contagion.

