### **Exclusion criteria:**

- 1.- Persons with incomplete vaccination schedule against COVID-19.

Persons who have 30 +/- 5 days after having completed the COVID-19 vaccination schedule.

- 3.- People under treatment with any immunosuppressive drug.
- 4.- Persons who refuse to sign the informed consent.

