#### **Elimination criteria:**

- 1.- Subjects who during the study develop COVID-19.
- 2.- Subjects who decide to leave the study before the stipulated time for the collection of the required blood samples.

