#### **Procedure:**

(a) Participants were selected by clinical history to assess current health status, obtain demographic data, as well as personal pathological history of importance for the study (chronic degenerative diseases, history of COVID-19 disease).

b) Peripheral venous blood samples (3 ml per occasion) will be taken from all participants. They will be carried out on days 30,60 and 120 after completion of the COVID-19 vaccination schedule.

c) Sample processing:

tRNA extraction from all samples.

cDNA synthesis

Real time PCR performance.

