### **Statistical analysis**

Descriptive phase: The results were presented in tables for continuous variables with normal distribution in measurements  $\pm$  standard deviation and for free distribution in medians and percentiles. While the categorical variables were presented in percentages and total figures.

Bivariate phase: To look for differences in the quantitative variables according to the Kolmogorov-Smirnov normality test, the student t test or the Mann-Whitney U test were used or for the related ordinal variables the Wilcoxon test. The dichotomous or ordinal related qualitative variables were analyzed with the McNemar test, for the dichotomous or ordinal variables not related they were analyzed with the chi square test or Fisher's exact test.

Multivariate phase: To compare and find the differences in more than two groups in the quantitative variables with free distribution the Kruskall-Wallis test; for the related samples with free distribution the Friedman test was used. All calculations were performed using the current version of the SPSS statistical package for Windows and the Jamovi program version 4.1 of R. Statistical significance was considered to be a P value  $<0.05$  and a confidence interval of 95%.

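### The plan cannot test its hypothesis on preventing re-contagion: no necessary level is defined, infection is not an outcome, and people who develop COVID-19 during the study are eliminated

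*Combined protocol and SAP*

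**What the plan says.** The Hypothesis section holds the only hypothesis: that anti-spike IgG gene expression in fully vaccinated people "does not develop the necessary immunogenicity in the Mexican population to prevent re-contagion". The Problem Statement likewise presents infection after vaccination as the question behind the study.

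The rest of the plan is about expression:

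- **Objectives.** The General Objective is to characterise expression. The Specific objectives concern how the virus is transmitted at the cell, identifying the study population, and identifying the IgG genes.
- **Procedure.** A clinical history at selection includes "history of COVID-19 disease". Of the blood samples, the plan says "They will be carried out on days 30,60 and 120 after completion of the COVID-19 vaccination schedule". The samples then go through RNA extraction, cDNA synthesis and real-time PCR.
- **Elimination criteria.** The first criterion is "Subjects who during the study develop COVID-19".
- **Statistical analysis.** The section lists generic two-group, paired and multi-group tests, for example "To compare and find the differences in more than two groups in the quantitative variables with free distribution the Kruskall-Wallis test", and the Friedman test for related samples.

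There are four vaccine groups of 20. Everyone is vaccinated.

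**The concern.** A claim that a response is not enough to prevent infection can be tested in two ways. Either a level that counts as enough is fixed in advance and the data are compared with it, or infection is observed and related to the response measured beforehand. The plan does neither, and the event that would show protection failing is a reason to leave the study.

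What is at stake is the conclusion. A significant or null difference between vaccines could be reported as evidence that they do or do not prevent re-infection, although the study measured nothing that bears on it. These four vaccines are compared because people have received them, so such a statement would carry weight.

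**Working it through.** The documents state no power, effect size, SD or event rate, so there is no figure of theirs to reproduce. The main check is what the hypothesis needs against what the plan contains.

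**1. Needs against contents**

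| Needed to test the hypothesis | What the plan has |
|---|---|
| A necessary level or decision rule | None in any section from Hypothesis to Statistical analysis |
| Infection as an outcome | Not in the General or Specific objectives |
| Case definition and surveillance | None; Procedure schedules no infection testing |
| A test against a level, or of expression against later infection | None; the listed tests compare groups or related measurements |
| Infected participants in the data | Those who develop COVID-19 during the study are eliminated |

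The planned tests can say that expression differs, or is not shown to differ, between vaccines or days. Neither answer says whether expression is sufficient.

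**2. What elimination does.** The plan does not say whether eliminated participants leave the analysis. If they do, no detected on-study case remains. Undetected cases may remain, because the COVID-19 section says of the clinical presentation that "it can range from asymptomatic to extremely severe" and no testing is scheduled. People with COVID-19 before enrolment meet no exclusion or elimination criterion. Their history is recorded, but the Statistical analysis section gives it no role. Infection before sampling also could not show whether the expression measured later protects.

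**3. Would keeping infected participants be enough?** Not by itself: finding lower expression in the infected would be an association, and would still not define the level that is enough. Precision is a second matter. The documents give no infection rate, so assume 2%, 5%, 10% and 20% during follow-up. With N = 4 × 20 = 80 the expected numbers are 80 × 0.02 = 1.6 (taken as 2), 80 × 0.05 = 4, 80 × 0.10 = 8 and 80 × 0.20 = 16.

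For a two-sample t test (two-sided 0.05, power 0.80, 78 degrees of freedom) the required noncentrality is 2.837. With k infected and 80 − k uninfected, the detectable difference in SD units is d = 2.837 × √(80 / [k(80 − k)]).

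| k infected | 80 − k | √(80 / [k(80 − k)]) | d |
|---|---|---|---|
| 2 | 78 | 0.716 | 2.03 |
| 4 | 76 | 0.513 | 1.46 |
| 8 | 72 | 0.373 | 1.06 |
| 16 | 64 | 0.280 | 0.79 |

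**4. Selection by elimination, worst case.** Suppose expression is normal on the analysis scale and everyone eliminated has the lowest values. Removing the lowest fraction p = k/80 raises the mean of the rest by about φ(z_p)/(1 − p) SD, where φ is the standard normal density and z_p the p quantile:

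- k = 2: 0.0584 / 0.975 = 0.060
- k = 4: 0.1031 / 0.95 = 0.109
- k = 8: 0.1755 / 0.90 = 0.195
- k = 16: 0.2800 / 0.80 = 0.350

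Simulation at n = 80 gives 0.06, 0.11, 0.19 and 0.35 SD. If 2 of the 20 in one vaccine group are removed, the simulated bound for that group is 0.18 SD. These are upper limits, not expected values.

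**The case against.** The strongest reply is that the study is descriptive. The General Objective asks only for characterisation of expression, the planned comparisons can be run, and elimination has a sound purpose: a sample taken after infection mixes infection-induced with vaccine-induced response. All of that stands, and it limits the consequence to the hypothesis and to any conclusion drawn from it. It does not rescue the hypothesis, which is about protection and which a reader would expect the study to answer.

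Four stronger readings are tempting, and the documents do not support them:

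- *All COVID-19 cases are kept out.* Only cases arising during the study are eliminated; people with earlier COVID-19 may enter.
- *Eliminated participants certainly leave the analysis.* The plan does not say so, which is why the selection argument is conditional.
- *Eighty people are too few to relate expression to infection.* That depends on the unknown infection rate. With 16 infected, about 0.8 SD is detectable. The firmer reason is that even a detected difference would not define sufficiency.
- *Elimination seriously biases the comparisons.* The figures are worst-case bounds, and no realistic case can be worked out from the documents.

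**Conclusion.** The concern holds. The plan, followed exactly, cannot support or refute its stated hypothesis. This rests on reading the design sections and on no assumed number. It is more than missing detail, because the design cannot answer the question posed.

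The secondary figures rest on assumptions. The detectable differences of about 2.0, 1.5, 1.1 and 0.8 SD assume 2, 4, 8 and 16 infected of 80 and normal-theory tests. The selection shift of at most about 0.06 to 0.19 SD for 2 to 8 of 80 removed assumes removal from analysis, normality, and that those removed had the lowest expression.

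The descriptive objective survives, so this should be corrected but does not undo the study.

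**What to change.** 1. Restate the hypothesis as something the data can test, for example: anti-spike IgG mRNA expression differs between the four vaccine groups and changes across the sampling days. Analyse it with the tests in the Statistical analysis section.
2. State that no conclusion will be drawn on protection from re-contagion.
3. Report, for each vaccine group, how many participants were eliminated for COVID-19, and say that the count may be incomplete because detection is unspecified.
4. Keep these participants' pre-infection samples in the descriptive summaries only. Later samples would mix the two sources of response, and people with an incomplete series cannot enter a complete-case Friedman test. If they are removed from the comparisons, note that those comparisons are selected towards people not known to be infected.
5. Label the restated hypothesis post hoc if any data were analysed before the change. The mixed tenses in the Procedure and Statistical analysis sections do not settle this.

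**Cost.** Protocol wording, one tally, and the use of samples already taken; no new participants or assays. The operation of the elimination criterion changes slightly. The re-contagion question is given up, although this design cannot answer it.

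Two neighbouring matters are separate points and not part of this one: reconciling the exclusion window around day 30 with the day-30 sample, and naming a test for more than two groups when the data pass the normality check.

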## **General Objective**

To characterize the immunogenicity induced by COVID-19 vaccines in Mexican population: mRNA expression for IgG anti-spike.

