## **Specific objectives**

1. Determine the mechanisms of virus transmission on the cell.
2. To identify the study population.
3. To identify the anti-spike IgG genes in vaccinated population.

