### Schedule

Stage 1	Stage 2	Stage 3
Sample collection	Experimental	Analysis of results and re writing.
Duration: 4 months (September December 2021)	Duration: 4 months (January-February 2022)	Duration: 3 months (May-2022)

Collection and transport of bl samples from all selected participants.
 
✓ Extraction of tRNA from bl samples.
 
✓ cDNA synthesis.
 
✓ Real-time PCR.
		

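### The only outcome is named as anti-spike IgG mRNA expression, but the assay as described states no PCR target and has no spike-selective step, so it cannot be shown to measure that outcome

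*Combined protocol and SAP*

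**What the plan says.** The outcome is named in three places, each time as specific to spike:

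- Hypothesis: "Gene expression for IgG anti-spike in subjects with a complete vaccination schedule against COVID-19" is what the study expects to fall short.
- General Objective: "To characterize the immunogenicity induced by COVID-19 vaccines in Mexican population: mRNA expression for IgG anti-spike".
- Specific objectives, item 3: "To identify the anti-spike IgG genes in vaccinated population".

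The laboratory method is in the Procedure section. The specimen: "Peripheral venous blood samples (3 ml per occasion) will be taken from all participants", on days 30, 60 and 120 after the vaccination schedule is completed. The processing has three lines: "tRNA extraction from all samples", "cDNA synthesis" and "Real time PCR performance". The Schedule repeats these steps, starting from "Extraction of tRNA from bl samples". The Statistical analysis section lists tests and a significance level but does not define the outcome variable.

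**The concern.** Real-time PCR amplifies whatever its primers match, so the primers decide what the result means, and none are stated. The gap goes beyond missing detail. An antibody's specificity for spike lies in its rearranged variable region, which differs between B-cell clones and between people. The IgG sequence that participants share is the constant region, which is the same whatever the antibody binds. (This is general immunology, not something the documents state.) Naming a conventional IgG primer pair would therefore not make the result anti-spike.

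The meaning of the study's only outcome is at stake. If the signal covers all IgG, a real difference between vaccines in the spike-specific response could be diluted. Equally, a difference in unrelated IgG transcription between groups could be published as a difference in anti-spike immunogenicity. Since the Hypothesis predicts inadequate immunogenicity, a flat result from a non-specific signal could also be misread as support for it.

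**Working it through.** **Step 1. Outcome against assay.** The plan states no figure that could be reproduced here: there is no power calculation, effect size or standard deviation. The check is therefore a reading of every section that describes outcome, specimen, assay or analysis.

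| Needed for an anti-spike claim | What the plan gives |
|---|---|
| A PCR target, with primers or probe | Not stated |
| Reference gene and quantification rule | Not stated |
| Selection of spike-binding B cells, or antigen stimulation | No such step in Procedure or Schedule |
| Sequencing of the antibody repertoire | No such step |
| Anti-spike antibody in serum or plasma | Not measured |
| A pre-vaccination sample to show background IgG | None; days 30, 60 and 120 after vaccination only |

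No other section supplies a missing item.

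**Step 2. How far dilution could go (illustration only).** Suppose the PCR target is shared by all IgG. Let f be the spike-specific share of IgG transcripts in the lower-responding vaccine group, and let the other group have k times as many spike-specific transcripts, all else equal. Then

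ratio of total IgG transcripts = (1 − f) + f·k = 1 + f(k − 1).

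With k = 10 this is 1 + 9f. On the PCR scale the difference is log2(1 + 9f) cycles, against log2(10) = 3.32 cycles for the spike-specific part alone. Both f and k are assumptions; the documents give neither.

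To see what 20 people per group (from the list of study groups) could detect, take approximate pairwise power as Φ(δ / (SD·√(2/20)) − 1.96). Here δ is the difference in cycles, with two-sided alpha 0.05 (the plan gives 0.05 but not the sidedness). The formula counts only rejections in the correct direction, so its floor is 0.025. The SDs of 0.5 and 1.0 cycle are also assumptions.

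| f | 1 + 9f | Cycles | Power, SD 1.0 | Power, SD 0.5 |
|---|---|---|---|---|
| 0.1% | 1.009 | 0.01 | 0.03 | 0.03 |
| 1% | 1.09 | 0.12 | 0.06 | 0.12 |
| 5% | 1.45 | 0.54 | 0.40 | 0.92 |

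Measured directly, the 10-fold spike-specific difference would have power of about 1.00 at either SD.

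**Step 3. Sensitivity to the definition of f.** If f is instead the share in the higher-responding group, the ratio is 1 / (1 − 0.9f). This gives 1/0.9991 = 1.001, 1/0.991 = 1.009 and 1/0.955 = 1.05 at f = 0.1%, 1% and 5%. The dilution is then stronger, so the definition of f must accompany any figure quoted.

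**The case against.** The strongest objection is that the plan names no primers, so nobody can say what the assay would amplify. A reader might infer that the study will measure total IgG heavy-chain mRNA from whole blood and label it anti-spike. The documents do not support that as a statement of fact. They mention neither heavy chain, constant region nor total IgG. They say peripheral venous blood and list no cell separation, which makes a whole-blood reading plausible but does not state it. The term tRNA may mean total RNA. This objection stands, and the claim is limited accordingly: specificity is not shown, and conventional IgG primers would not provide it.

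A second objection is that the plan has some safeguards against unrelated immune activity. People on immunosuppressive drugs are excluded, participants who develop COVID-19 during the study are eliminated, and current health, chronic disease and COVID-19 history are recorded. Moreover, non-specific transcription that is similar in all groups adds noise and dilution, not a false difference. This also stands in part. A false difference needs imbalance between groups. The groups are formed by vaccine received, with no randomisation described and no adjustment planned, so imbalance is possible but not established. None of the safeguards makes the assay specific.

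A third objection is that the magnitude is hypothetical. That is correct: f, the fold difference and the SDs are all assumed. At f = 5% with an SD of 0.5 cycle, a 10-fold difference would still usually be detected. The numbers show what could happen, not what will.

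**Conclusion.** The concern holds in a limited form. The only named outcome is anti-spike IgG expression, and the assay as described cannot be shown to measure it. With conventional IgG primers, it would measure IgG transcripts of all specificities. That conclusion comes from setting the sections side by side and from where antibody specificity resides; it does not depend on the illustration.

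The size cannot be fixed from the documents. Under a 10-fold contrast, with f as the share in the lower-responding group, a total-IgG signal would differ by a factor of 1.009 to 1.45 for f between 0.1% and 5%. The point matters because there is no second outcome to fall back on: followed as written, the plan would attach an unsupported label to its one result and carry that label into a comparison of four vaccines.

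**What to change.** 1. In the Procedure section, state the PCR target (primers or probe and the region amplified) and the reference gene.
2. In the Hypothesis, General Objective and specific objective 3, name the outcome for what that target measures. If it is an IgG constant-region target, for example: *IgG transcript expression in peripheral blood*. The new name should follow from item 1, not precede it.
3. Add a statement that the PCR result will not be reported as an anti-spike or spike-specific response, nor used alone to conclude on vaccine immunogenicity.

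These are text changes and need no new samples. They do have a price: the hypothesis and general objective become narrower, because the study would have no spike-specific measurement.

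Optional, and not part of the inexpensive fix: if suitable serum or plasma remains, add a quantitative anti-spike IgG binding assay, on at most 80 × 3 = 240 samples. It needs extra resources. The Procedure gives 3 ml per occasion but no tube type or plasma handling, so availability of the sample must be confirmed first.
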